#### **Relevant Co-Morbidities Before HES Administration**

Operational definitions for the below listed variables (co-morbidities) are given in Annex 5, apply for this DUS only and must be considered when the information for the respective variable is to be entered in the eCRF from patient charts.

- Hypersensitivity to HES or to any of the other excipients in the HES product (yes/no)
- Burns (yes/no)
- Disturbed fluid status (yes/no)
  - Dehydration (yes/no)
  - Hyperhydration (yes/no)
- Severe hyperkalaemia (yes/no)
- Severe hypernatraemia (yes/no)
- Severe hyperchloraemia (yes/no)
- Congestive heart failure (yes/no; if yes: NYHA stage)
- Pulmonary oedema (yes/no)
- Severely impaired hepatic function (yes/no)
- Renal failure
  - Renal impairment (yes/no)
  - Renal replacement therapy (yes/no)

- Severe coagulopathy (yes/no)
- Systemic inflammation
  - Sepsis (yes/no)
  - Severe sepsis (yes/no)
  - Septic shock (yes/no)
- Clinically relevant intracranial/cerebral bleeding (yes/no)
- Organ transplant patient (yes/no)
  - Acute organ transplant patient (yes/no)
  - Date of transplantation, if available (calendar week, year)

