##### **Rationale and Background**

The European Medicines Agency (EMA) Pharmacovigilance Risk Assessment Committee (PRAC) recommended in the Article 107i procedure according to Directive 2001/83/EC for HES-containing medicinal products (EMA/H/A-107i/1376) in October 2013 that HES solutions must no longer be used to treat patients with sepsis or burn injuries or critically ill patients because of an increased risk of kidney injury and mortality while the benefit-risk ratio for HES-containing medicinal products remains favourable in the treatment of hypovolaemia due to acute blood loss when crystalloids alone are not considered sufficient.

The final implementing decision, issued by the European Commission (EC) on December 19, 2013, implicates new contraindications, new special warnings and precautions for use as well as other changes to the European Product Information (PI) [Summary of Product Characteristics (SmPCs); Package Leaflet] for risk minimisation measures (as requested in Annex III of this EC decision).

To “evaluate the effectiveness of the risk minimisation measures taken” (as requested in Annex IV of the EC decision), the concerned MAHs of HES products subject to the PRAC procedure were asked to conduct a Drug Utilisation Study (DUS) with HES-containing medicinal products in several European Union (EU) Member States.

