## 7. Rationale and Background

Following the publication of investigator initiated clinical trials such as 6S (Perner et al. 2012), CHEST (Myburgh et al. 2012) and VISEP (Brunkhorst et al. 2008), comparing HES-containing solutions with crystalloids in critically ill patients (e.g. septic patients), the EMA, initiated procedures to assess the benefits and risks of HES-containing solutions, especially in critically ill patients.

In the relevant European referral procedure according to Article 107i of Directive 2001/83/EC for HES-containing medicinal product (EMEA/H/A-107i/1376) the PRAC, recommended in October 2013 that HES-solutions must no longer be used to treat patients with sepsis or burn injuries or critically ill patients because of an increased risk of kidney injury and mortality in these patients but that the benefit-risk ratio for HES-containing

medicinal products remains favourable in the treatment of hypovolaemia due to acute blood loss when crystalloids alone are not considered sufficient.

This recommendation was adopted by majority vote by the Coordination Group for Mutual Recognition and Decentralised Procedures human (CMDh). The final implementing decision was issued by the EC on December 19, 2013 by which this referral procedure was positively concluded. This implicates new contraindications, special warnings and precautions for use as well as other changes to the European PI for risk minimisation measures (as requested in Annex III of the EC decision).

In addition, the concerned MAHs were requested to conduct a DUS with HES-containing medicinal products in several EU Member States to “evaluate the effectiveness of the risk minimisation measures taken” (as requested in Annex IV of the EC decision).

The DUS will be performed by the MAH Fresenius Kabi Deutschland GmbH and will include all available HES-containing medicinal products of this MAH in those European countries where the DUS will be performed. A detailed overview about the concerned medicinal products in the individual country is provided in Annex 1a.

In summary, the scope of this DUS is to investigate the adherence of hospital physicians to the revised European PI for HES-containing medicinal products during routine administration of HES-solutions in hospitals to evaluate the effectiveness of the risk minimisation measures taken.

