## **8. Research Question and Objectives**

The objective of the DUS is to assess the adherence of hospital physicians to the revised European PI for HES-containing medicinal products concerning indication, posology (dosage), and contraindications (as listed in Annex III of the EC decision).

In general, due to its retrospective and non-interventional nature the DUS can only be used to generate hypotheses and not to test any a-priori specified hypothesis.

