##### **Basic Assessment**

- Hospital (name, address)
  
- Patient admission date (calendar week, year)

- Ward(s) where HES of Fresenius Kabi was administered
  - ICU (if various, specify)/PICU/Operating room/Surgical ward/Intermediate care/Emergency unit/Burns unit/Other
- Demographic data
  - Age (< 18 years or ≥ 18 years)
  - Weight
- Main diagnosis at hospital admission (ICD-10 code plus corresponding plain diagnosis text)
- Indication for HES use
  - Treatment of Hypovolaemia due to acute blood loss (yes/no)
  - Treatment of Hypovolaemia without acute blood loss (yes/no)
  - HES used exclusively for “Prophylaxis of Hypovolaemia” and not for “Treatment of Hypovolaemia” (yes/no)
  - Other (yes/no; if yes ICD-10 code)

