### **9.6.2 Patient Data Anonymisation**

Patient data investigated will be de-identified in an unlinked manner to personal identifier. The documented data are restricted to personal identifier, patient age range (< 18 years or ≥ 18 years), medical procedures, diagnostic codes according to ICD-10, and name, dose, and duration of supply of prescribed HES product (and other drugs, if applicable). The full list of anonymised patient specific variables is specified in [Section 9.3.2](#).

Fresenius Kabi will in no way be able to backtrace the identification of any study subject.

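### Critically ill patients are named as a group barred from HES, but no recorded variable identifies them, so non-compliance may be understated

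*Protocol*

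**What the plan says.** The rationale in Protocol Section 7 states that "HES-solutions must no longer be used to treat patients with sepsis or burn injuries or critically ill patients", and the abstract (Section 4) repeats this almost word for word. Section 8 sets the objective as physicians' adherence to the revised product information on indication, posology and the contraindications in Annex III of the EC decision.

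Section 9.3.2 lists what is recorded per patient. Its co-morbidity part has an item for burns and three for systemic inflammation, the last being "Septic shock (yes/no". It introduces the definitions with "Operational definitions for the below listed variables (co-morbidities) are given in Annex 5, apply for this DUS only". Section 9.6.2 treats Section 9.3.2 as exhaustive: "The full list of anonymised patient specific variables is specified in" that section. The nearest item to critical illness is the ward or wards where HES was given, under Basic Assessment: "ICU (if various, specify)/PICU/Operating room/Surgical ward/Intermediate care/Emergency unit/Burns unit/Other".

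Section 9.7.1 says that patients whose HES use departs from the revised product information will be counted, with percentages and 95 % confidence intervals. It leaves the detailed analysis to a later SAP.

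**The concern.** The study exists to show whether the risk minimisation measures work. Section 7 traces the whole referral to trials in the critically ill, with septic patients given as an example of that group. Two of the three restricted groups have their own eCRF item; the third and broadest has none.

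A missing variable differs from a missing analysis rule. A SAP can define how recorded items are combined, but it cannot supply an item that nobody extracted. Section 9.6.2 de-identifies the data without a link to the patient, and Section 9.9 says the CRO cannot check entries against the original records. Going back for the information after extraction is therefore not a realistic route. At stake is a direct adherence figure for a restriction central to the study's own rationale, together with a possible downward bias in overall non-compliance.

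**Working it through.** **Step 1. Set the restricted groups against the recorded items.**

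- Sepsis: restricted in Sections 4 and 7. Recorded in Section 9.3.2 at three levels of severity.
- Burns: restricted in Sections 4 and 7. Recorded in Section 9.3.2.
- Critically ill: restricted in Sections 4 and 7. No item in any part of Section 9.3.2 (basic assessment, co-morbidities, HES before admission, HES in the hospital, completion).

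Some recorded items overlap with critical illness: renal replacement therapy, renal impairment, severe coagulopathy, sepsis and the ward. Section 9.3.2 has no ventilation, vasopressor or severity-score item. The protocol does not say that any item or combination stands for critical illness.

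**Step 2. Identify who is missed.** Non-compliance covers contraindication, indication and posology. A critically ill patient who also has sepsis, was treated without acute blood loss, or received a deviating dose can still be counted on that other ground. The patients at issue are those who are critically ill and have no other recorded deviation of any kind. Call their share of all HES patients *c*. The documents give no value for *c*.

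**Step 3. Reproduce the plan's precision figures.** Section 9.5 uses the exact binomial interval. With x events in N patients, the lower limit is the 2.5 % quantile of Beta(x, N − x + 1) and the upper limit is the 97.5 % quantile of Beta(x + 1, N − x). At an assumed rate of 3 %:

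- N = 3000, x = 90: 2.42 to 3.67 %. The plan states 2.4 to 3.7 %.
- N = 334, x = 10: 1.44 to 5.44 %. The plan states 1.4 to 5.4 %.

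Both agree.

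**Step 4. Illustrate the effect.** Assume that recorded non-compliance is 3 % and that the patients in *c* are not flagged. Then true rate = 3 % + *c*, while the reported interval stays as in Step 3.

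| *c* (assumed) | True rate | Inside 2.4 to 3.7 % (N = 3000)? | Inside 1.4 to 5.4 % (N = 334)? |
|---|---|---|---|
| 0.5 % | 3.5 % | yes | yes |
| 1 % | 4 % | no | yes |
| 2 % | 5 % | no | yes |
| 3 % | 6 % | no | no |
| 5 % | 8 % | no | no |

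The overall interval fails once *c* exceeds 3.67 − 3.00 = 0.67 percentage points, which is about 0.0067 × 3000 = 20 patients. The country interval fails once *c* exceeds about 5.44 − 3.00 = 2.44 points, or about 0.0244 × 334 = 8 patients. Had the 1 % been captured, the overall result would read 4 % with an interval of 3.3 to 4.8 %.

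The reported intervals cover sampling error only. A larger sample narrows them without reducing this error, so the pooled estimate is the more exposed of the two.

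**The case against.** A reader might go further and infer that the plan scores HES use in critically ill patients as adherent. The documents do not support that. No section contains a classification rule, the SAP is not shown, and mapping recorded items to adherence is ordinary SAP content. That no rule ties the ICU to a contraindication is therefore not itself a fault.

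Nor is it right that nothing at all can be reported. The ward is recorded, so a proxy rate for HES given on an ICU or PICU is available without new data. The proxy is imperfect in both directions: ICU patients are not all critically ill, and critically ill patients treated in the operating room or emergency unit would be missed. It narrows the gap without closing it.

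Section 9.6.2 also mentions procedures and other drugs in general terms, which might suggest organ-support data. But it refers to Section 9.3.2 for the full list, and no ventilation or vasopressor item is there.

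Two further limits stand. The texts of Annex III and Annex 5 are not available, so how the restriction is worded, and whether Annex 5 goes beyond its stated scope, cannot be checked. And the 1 to 4 % rates in Section 9.5 illustrate interval width; they are not a forecast, so no fraction of them can be called hidden.

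What survives is that a named restricted group has no direct variable in a list the protocol calls full.

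**Conclusion.** The point holds in this form. Adherence to the restriction on critically ill patients cannot be measured directly with the listed variables. Critically ill patients with no other recorded deviation cannot be identified as non-adherent by any stated variable. Taken alone, this omission can only lower measured non-compliance. The amount is unknown.

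The figure of a true 4 % against a reported 2.4 to 3.7 % rests on three assumptions: a 3 % recorded rate, a 1 % share of such patients, and no use of the ward to flag them. One point lost for each percent of patients is the full effect only for patients with no other deviation; for critically ill patients in general it is an upper bound. The conclusion also rests on the protocol's own account of the restriction and of the scope of Annex 5. It should be corrected before extraction, because the SAP cannot restore the item later.

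**What to change.** Before chart extraction starts:

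1. Add to the co-morbidity list in Section 9.3.2 the item *critically ill before HES administration (yes / no / not documented)*.
2. Add an operational definition to Annex 5, taken from the wording of Annex III.
3. Report contraindication non-compliance with this item included, and show how many patients are not documented.
4. Tabulate separately the patients given HES on an ICU or PICU, from the ward item already collected. Label this an imperfect proxy and do not equate it with non-adherence.

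Cost: one extra eCRF field and one definition. The field depends on what the charts contain and, like the rest of the data, cannot be source-verified by the CRO. The ward tabulation needs no new data. Measured non-compliance may rise.

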### **Variables**

The DUS will document patient data describing the medical status at initiation of treatment, posology (dosage) and contraindications of HES to identify deviations from the revised European PI (as listed in Annex III of the EC decision).

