The retrospective data collection will comprise patient chart data of patients who have been treated between January 1st, 2015 and May 1st, 2015. Patient chart data will be collected going backwards in a predefined timeframe, e.g. of one week (depending on the results of the site feasibility), starting May 1st, 2015 (calendar week 18). All patients treated with HES-containing products of Fresenius Kabi during this week should be documented. In the event that the predefined number of patients per site is not achieved within e.g. this week, data collection can be extended e.g. week by week (again going backwards) until the number of predefined patients has been reached, but not beyond January 1st, 2015. All patients treated with HES-containing products of Fresenius Kabi within the predefined timeframe are documented in the DUS and followed-up until the start and end of HES therapy, even if the start or end of HES therapy are outside the predefined timeframe.

Data collection will include relevant demographic data, main diagnosis at hospital admission, indication for HES use, posology (dosage), and co-morbidities.

The parameters as listed in [Section 9.3](#) will be documented.

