#### **HES Administration Prior to Admission to the Hospital (DUS Study Site)**

- HES administration at day of admission or preceding day before admission to the hospital (yes/no/no information available);  
if yes:
  - Place/institution [hospital, ambulance, other],
  - Trade name of any prescribed HES product
  - Posology (Dosage)
    - HES infusion (first to last bag/bottle)
      - Start of infusion (Day 1/Time hh:mm)
      - Total amount infused (ml)
      - End of infusion (Day X/Time hh:mm)

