#### **HES Administration in the Hospital (DUS Study Site)**

- Trade name of prescribed HES product
- Posology (Dosage)
  - HES infusion (first to last bag/bottle)
    - Start of infusion (Day Y/Time hh:mm) of each bag/bottle
    - Amount infused (ml) of each bag/bottle
    - End of infusion (Day Z/Time hh:mm) of each bag/bottle

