### **9.8.2 Procedures at the Contract Research Organisation (CRO) to Ensure Reliable Data Quality**

As far as possible, data will be checked automatically for completeness and accuracy on entry into the eCRFs (plausibility check by means of automatic queries). Missing or implausible values are highlighted and the staff member(s) in the participating sites will be prompted to confirm the correctness and completeness of the entered data.

All requests to complete missing data fields in the eCRF will be shown during data entry to the sites by the electronic data capture system, so that sites can readily access individual patient data to complete data if necessary.

Qualified English speaking personnel at the CRO will be available during all regular working hours (9am-5pm) to answer any immediate technical or procedural questions by the investigators from the sites.

All data will be prepared, anonymised and stored in data formats that are suitable for external auditing and inspection at any time the need should arise.

The CRO is responsible for performing eCRF training and providing all relevant documentation to the investigator and delegated responsible persons at each site as specified in [Section 9.8.1](#).

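### Contraindication items cannot separate absent from not documented and are taken only before HES, so non-adherence may be understated by an unknown amount

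*Protocol*

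**What the plan says.** The only outcome is adherence to the revised product information on indication, posology and contraindications (Protocol 8 and 9.1). The contraindication-type conditions are listed in 9.3.2 under "Relevant Co-Morbidities Before HES Administration". Each is answered yes or no, as in "Severe hyperkalaemia (yes/no". Operational definitions for these items are placed in Annex 5, whose text is not in the material at hand.

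The next block of 9.3.2 is built differently. It asks for "HES administration at day of admission or preceding day before admission to the hospital (yes/no/no information available", so the protocol allows there for a chart that says nothing.

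Exposure is followed much further than clinical status. Under 9.1, patients are "followed-up until the start and end of HES therapy, even if the start or end of HES therapy are outside the predefined timeframe". The in-hospital block of 9.3.2 asks for "Start of infusion (Day Y/Time hh:mm) of each bag/bottle", with end time and amount for each. The only item listed at completion of HES is the date of discharge from the treating ward.

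On data quality, 9.8.2 states: "Missing or implausible values are highlighted and the staff member(s) in the participating sites will be prompted". Section 9.7.1 adds that data still missing after the checks are not imputed. Section 9.9 rules out source data verification by the CRO. Section 9.7.2 claims that the retrospective design will bring to light use both within and outside the label.

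**The concern.** There are two separate gaps in what is collected.

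The first is the answer format. Several items, such as the three electrolyte disturbances, normally need a laboratory value. If none was taken, or the condition was not charted, the person abstracting the chart can enter no or leave the field blank. A blank triggers a prompt, which favours a definite answer. A no entered for want of evidence looks the same as a true absence, and without source data verification it cannot be found later.

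The second is timing. Posology is assessed over the whole course, contraindications only before it. If a listed condition such as sepsis or renal replacement therapy begins after the first bag and HES continues, the listed variables do not show it. Section 7 gives kidney injury and mortality in septic, burned and critically ill patients as the reason for the label change, so this part of use bears directly on whether the risk minimisation worked.

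Both gaps would make adherence look better than it is. An analysis plan written later cannot recover a distinction or a time point that the eCRF did not collect, so this is a matter for the protocol.

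**Working it through.** **1. The plan's own precision.** Section 9.5 gives exact 95 % intervals for an assumed non-compliance rate of 3 %. Clopper-Pearson limits with x = N × 0.03, rounded, reproduce them:

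| N | x | Computed | Protocol |
|---|---|---|---|
| 334 | 10 | 1.44–5.44 % | 1.4–5.4 % |
| 3000 | 90 | 2.42–3.67 % | 2.4–3.7 % |

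These intervals express sampling error only.

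**2. If non-adherent patients are missed.** Let p be the true rate and s the share of truly non-adherent patients who are not recognised, through either gap. The expected observed rate is p(1 − s). The documents give no value for s, so the range below is assumed. With p = 3 %:

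| s | Observed rate | 95 % interval, N = 334 | 95 % interval, N = 3000 |
|---|---|---|---|
| 10 % | 3 × 0.9 = 2.7 % | 1.24–5.05 % (9/334) | 2.15–3.34 % (81/3000) |
| 20 % | 3 × 0.8 = 2.4 % | 1.04–4.66 % (8/334) | 1.88–3.01 % (72/3000) |
| 30 % | 3 × 0.7 = 2.1 % | 0.85–4.27 % (7/334) | 1.62–2.68 % (63/3000) |
| 50 % | 3 × 0.5 = 1.5 % | 0.49–3.46 % (5/334) | 1.10–2.00 % (45/3000) |

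From about s = 21 % the pooled interval (71/3000: 1.85–2.98 %) lies wholly below the true 3 %. For one country of 334 this takes about s = 66 % (3/334: 0.19–2.60 %). The larger sample does not reduce the bias; it makes the interval around the biased value narrower.

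**3. If the field is left blank instead.** Suppose a share u of patients is left missing and excluded, and missingness is unrelated to the condition. The expected rate then stays at 3 % and only precision falls. At u = 20 %, 8/267 gives 1.30–5.82 % and 72/2400 gives 2.35–3.76 %. How charts without information are entered therefore decides whether there is a bias or only a loss of precision, and the collected data would not show which had happened.

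**4. Timing, from the variable list.** Before HES: listed conditions, yes/no. During HES: product, times and amounts. At completion: ward discharge date. No clinical status is listed after the first bag, so the claim in 9.7.2 cannot be met for conditions that arise during therapy.

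**The case against.** A reader might infer that the eCRF forces a no wherever information is lacking. The documents do not say so. Section 9.7.1 lets data remain missing, 9.8.2 only prompts staff to confirm or complete, and the Annex 5 rules, which might settle how an untaken laboratory value is entered, are not shown. What stands is that silent charts can be entered as no undetected, not that they are.

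A reader might also infer that conditions arising during therapy are wrongly coded no, or that continued HES in these patients is wrongly counted as adherent. A no in a field about the time before HES is a correct entry. Whether later bags count as non-adherent depends on Annex III of the EC decision, which is also not shown. The defect is the missing later field.

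The Abstract is weaker support for the timing point than it looks. It promises "The DUS will document patient data describing the medical status at initiation of treatment, posology (dosage) and contraindications of HES", where the words on initiation may qualify medical status alone. The timing point therefore rests on the heading and variable list in 9.3.2. Section 11 says that off-label use will be documented in the eCRF. This is a general statement, and it adds no clinical status field to the list in 9.3.2 from which such use could be recognised.

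The illustration also has limits. Section 9.3.2 expects these parameters to be well documented because they are part of routine care, and severe states may be charted more often than their absence. The 3 % is for non-compliance overall, so a patient missed on one item may still be counted on another. The share s of non-adherent patients missed is therefore not the share with an undocumented item, and may be much smaller.

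**Conclusion.** The point holds as a risk of bias in one direction, not as a demonstrated error. The listed items do not separate absent from not documented, and no listed variable captures a contraindication that arises after HES has begun. If either gap operates through missed cases, non-adherence is understated. The amount cannot be derived from the documents. The fall from 3 % to between 2.7 % and 1.5 % rests on an assumed s of 10 % to 50 %. The point deserves action before data collection because the planning rates in 9.5 are only 1 % to 4 %, source data verification is excluded, and 9.9 concedes incomplete documentation for HES amounts only.

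**What to change.** 1. Add a not documented/not measured answer to each co-morbidity item in 9.3.2, in line with the pre-admission HES item. Report its frequency by item, and give non-adherence among patients with information.

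2. As a sensitivity analysis, give item-level bounds with not documented set to no and to yes. These can be wide: with 3 % among documented patients and 20 % not documented, the bounds are 0.8 × 3 = 2.4 % and 2.4 + 20 = 22.4 %. They should accompany the estimate, not replace it.

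3. For patients given HES after the first bag, add one conditional field: new listed condition before a later bag (yes/no/not documented; which; day). Classify those bags according to Annex III of the EC decision. If this is not feasible, limit the contraindication claim in 9.7.2 to treatment initiation and list the restriction in 9.9.

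The cost is one answer option per item, one conditional field, slightly longer chart abstraction and a wider reported range of uncertainty.
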